13.6 VIDEO CALLS

All trial visits will be conducted remotely using real-time video conferencing.

The site personnel who will conduct remote visits will be trained on how to conduct real-time video conferencing visits (e.g., trained on the use of telemedicine for remote clinical trial visits).

Both the researcher and the trial participant should confirm their respective identities with one another before engaging in a visit by showing a photo ID to the camera.

The date and time of a visit should be documented in the trial records.

13.7 LATE AND MISSED VISITS

If a participant fails to return for a scheduled study visit within the visit window defined in the study protocol but completes the visit prior to the beginning of the next visit window, that visit is considered to have been completed late. A protocol deviation should be documented on the appropriate eCRF.

If a participant fails to return for a scheduled study visit within the visit window defined in the study protocol and the next scheduled study visit window opens, that visit is considered to have been missed. A protocol deviation should be documented on the appropriate eCRF.

CONFIDENTIAL Page **42** of **69**

All attempts should be made to schedule the participant for the study visit as soon as possible so that it is captured late rather than missed completely.

13.8 UNSCHEDULED VISITS

Participants may be seen for unscheduled visits as needed. During the unscheduled visit, the Investigator will assess the participant's progress and perform the following:

- ClinROs
 - HDRS-17
 - MADRS
 - YMRS
 - C-SSRS
- Review of concomitant medications
- Record any new or updated adverse events and device deficiencies, if applicable

13.9 STUDY COMPLETION/DISCONTINUATION

The Primary Endpoints will be evaluated at 10 weeks. Participants will complete study participation at 10 weeks unless consented and enrolled in an additional 10-week open-label portion of the study. Participants enrolled in the open-label phase will complete the trial after 20-weeks.

14 DESCRIPTION OF STUDY PROCEDURES

DEMOGRAPHICS

At screening, participant baseline characteristics including, but not limited to, age and gender, will be recorded.

PAST MEDICAL HISTORY

At screening, each participant's past medical conditions and surgical procedures will be recorded.

PREGNANCY DETERMINATION

Prior to treatment, female participants of childbearing potential will be asked during the Screening visit whether they are pregnant or breastfeeding or plan to become pregnant or breastfeed during the trial.

CLINICIAN AND PATIENT REPORTED OUTCOME QUESTIONNAIRES (CLINROS/PROS)

The following Clinician or Patient Reported Outcome questionnaires will be completed and used to compare participant outcomes at follow-up time points compared to baseline:

Montgomery–Åsberg Depression Rating Scale (MADRS) - ClinRO

CONFIDENTIAL Page **43** of **69**

The Montgomery–Åsberg Depression Rating Scale (MADRS) is a ten-item diagnostic questionnaire which psychiatrists use to measure the severity of depressive episodes in patients with mood disorders.

Montgomery–Åsberg Depression Rating Scale (MADRS-s) - PRO

MADRS-s is a self-rating version of MADRS and correlates well with expert ratings. The MADRS-s instrument has nine questions, with an overall score ranging from 0 to 54 points. During the trial, each participant reports their MADRS-s score in the same way as normal customers would. The MADRS-s uses cut-off points detailed below to classify the severity of depressive symptoms:

- 0-12 points: None or very mild depression
- 13-19 points: Mild depression
- 20-34 points: Moderate depression
- ≥ 35 points: Severe depression

Hamilton Depression Rating Score (HDRS-17)

The HDRS (also known as the Ham-D) is the most widely used clinician-administered depression assessment scale. The original version contains 17 items pertaining to symptoms of depression experienced over the past week. The questionnaire is designed to be used by clinicians to rate the severity of depressive symptoms in adults by probing mood, feelings of guilt, suicide ideation, insomnia, agitation or retardation, anxiety, weight loss, and somatic symptoms.

Mini International Neuropsychiatric Interview (MINI) - ClinRO

The Mini-International Neuropsychiatric Interview (M.I.N.I.) is a short structured diagnostic interview, developed jointly by psychiatrists and clinicians in the United States and Europe, for DSM-IV and ICD-10 psychiatric disorders.

Columbia Suicide Severity Rating Scale (C-SSRS) - ClinRo

The Columbia Suicide Severity Rating Scale, or C-SSRS, is a rating scale to evaluate suicide risk. The scale identifies specific behaviors which may be indicative of an individual's intent to kill oneself.

Hamilton Anxiety Rating Scale (HAM-A) - ClinRo

The HAM-A was one of the first rating scales developed to measure the severity of anxiety symptoms and is still widely used today in both clinical and research settings. The scale consists of 14 items, each defined by a series of symptoms, and measures both psychic anxiety (mental agitation and psychological distress) and somatic anxiety (physical complaints related to anxiety).

Young Mania Rating Scale (YMRS) - ClinRo

The Young Mania Rating Scale (YMRS) is one of the most frequently utilized rating scales to assess manic symptoms. The scale has 11 items and is based on the patient's subjective report of his or her clinical condition over the previous 48 hours.

Rey Auditory Verbal Learning Test (RAVLT) - ClinRo

The Rey Auditory Verbal Learning Test (RAVLT) is a neuropsychological assessment designed to evaluate verbal memory in patients, 16 years of age and older. The RAVLT can be used to evaluate the nature and severity of memory dysfunction and to track changes in memory function over time.

Symbol-Digit Modalities Test (SDMT) - PRO

The Symbol Digit Modalities Test (SDMT) detects cognitive impairment. It is a way for clinicians to screen for organic cerebral dysfunction in both children (eight years and older) and adults. The SDMT is brief, easy to administer, and has demonstrated sensitivity in detecting not only the presence of brain damage, but also changes in cognitive functioning over time and in response to treatment.

Treatment Acceptability Questionnaire (TAQ) - PRO

TAQ is a questionnaire for probing how acceptable participants of tDCS clinical trial think the treatment is. At baseline it measures participant's expectations about the trial, e.g., treatment outcome, effort needed, ethics, etc., and then follow-up on these expectations at the end of the trial.

tDCS Adverse Events Questionnaire (AEQ) - PRO

AEQ is a specialized questionnaire developed to capture the adverse events during tDCS trials.

EQ-5D-3L - PRO

The EQ-5D-3L is a standardized measure of health-related quality of life.

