7 SCHEDULE OF PROCEDURES

Table 1. Schedule of Procedures. Activities in blue cells are performed by trained graduate researchers supervised by a trained psychiatrist, and red cells are to be completed by the participant.

	Pre-Treatme nt		E	Blinded Pha	ise		Open-La Phas	abel e	Early termination ⁸
Activity	Week -3 to -1 (± 3 days)	Week 0	Week 1 (± 3 days)	Week 4 (± 3 days)	Week 7 (± 3 days)	Week 10 (± 3 days) Final blinded visit ¹	Week 10 (± 3 days) Open Label Start	Wee k 20 (± 3 days)	Week 1-20
Informed Consent	х								
Screening and baseline Video Call	х								
Diagnostic Assessment for MDD	X٩								
Intervention Kit Shipped to subject	X ⁵								
Randomization ⁶		Х							
Technical onboarding		х							
Initial Visit		Х							
Video call	Х	Х	Х	Х	Х	Х		Х	Х
MINI	Х								
HDRS-17	X		X	Х	X	X		X	X
MADRS	Х		Х	Х	Х	Х		X	Х
MADRS-s	X	X ⁴	X	X	X	X		X	Х
C-SSRS	X		X X	X X	X X	X		X	X X
YMRS	X X		X	X	X	X X		X	X
HAM-A	X					X		X X	X
EQ-5D-3L RAVLT	X					X		X	X
SDMT	~	X ²				 X ²		Λ X ²	^
TAQ	X	~				X		X	Х
AEQ						X		X	X
Healthcare Visit Survey ³						X		X	X
FLOW FL-100 use ⁷		х	х	х	х	х	х	Х	
Record/Review Concomitant Medications	х	х	х	х	х	х		х	х
Record/Review Adverse Events		Х	Х	Х	Х	Х		Х	Х

CA-127-T1, v3.0 Flow Neuroscience AB, FL001 CONFIDENTIAL Page **19** of **69**

¹ The week 10 visit includes the study Primary end-point. This will be the final blinded visit and will be the start of the open label phase of the study. Participants in the Sham arm will be informed of their assignment and will restart with active stimulation for 10 weeks; participants in the Flow FL-100 arm will be allowed to continue maintenance treatment for 10 more weeks at 3 sessions per week. The unblinding will occur after the primary end-point data has been recorded. ² Optional

³ Participants will be surveyed about the number of times he/she has sought healthcare due to depression during the previous 10 weeks.

⁴ Participants will be required to answer the nine questions of the MADRS-s form in the app to start the first stimulation session during the technical onboarding.

⁵ Participants will be required to start treatment within 24 days from completing the baseline surveys.

⁶ Completed after eligibility is confirmed by the investigator; when the participant signs up with their email in the trial app they will automatically be randomized to the sham or active treatment arm (with 50% probability).

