- 21. Have been diagnosed with Parkinsonism or other movement disorder as determined by the investigator to interfere with treatment.
- 22. Have ever taken esketamine / ketamine for treatment of depression.
- 23. Have ever been admitted to hospital for depression.
- 24. Have ever been diagnosed with obsessive-compulsive disorder (OCD) or bipolar type 1 or 2 disorder.
- 25. Is diagnosed with an active primary anxiety disorder, or PTSD, agoraphobia, anorexia or bulimia, panic or personality disorder with active symptoms.
- 26. Have a history of psychosurgery for depression.
- 27. Have any history of myocardial infarction, coronary artery bypass graft (CABG), coronary heart failure (CHF), or history of other cardiac issues.
- 28. Are currently experiencing or have a history of intractable migraines.
- 29. Are a chronic tobacco smoker, as defined by smoking by smoking >100 cigarettes (including hand-rolled cigarettes, cigars, cigarillos, etc.) in their life-time and have smoked every day for the last 7 days.

- 30. If female and of child-bearing potential, currently pregnant or breastfeeding or planning to become pregnant or breastfeed any time during the study.
- 31. Are currently a prisoner.
- 32. Are participating concurrently in another clinical investigation or have participated in a clinical investigation within the last 90 days or intend to Participate in another clinical investigation during the study, and where the participation in the other investigation might interfere with the results of this trial as deemed by the PI.
- 33. Have any medical condition or other circumstances, in the judgment of the investigator, that might interfere with the ability to complete follow-up visits and the self-reported MADRS-s in the app.
- 34. Have any condition which, in the judgment of the Investigator, would preclude adequate evaluation of the device's safety and performance.
- 35. A Subject who meets any of the exclusion criteria during study participation will be discontinued from the study

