13 STUDY PROCEDURES

13.1 WEEK -3 TO -1: INFORMED CONSENT (ICF)

After passing the screener survey, prospective participants will be directed to review and sign an electronic HIPAA, and an IRB/EC-approved consent (eConsent) form that are hosted in the Curebase system. The eConsent form will explain the nature and scope of the study, the procedures to be performed as part of the study, the potential risks, and benefits of participation, expected duration of participation, possible treatment alternatives, and an overview of his/her rights as a study participant in lay terms. Participants will have the opportunity to discuss the study with their family or surrogates or think about it before agreeing to participate. Participants will be informed that participation is voluntary and will be assured that they may withdraw from the study at any time and for any reason, without repercussion.

After viewing the eConsent materials, participants will have an opportunity to email or call the research team with any questions they may have and will be given as much time as needed to receive answers before making a final decision regarding study participation. Participants will receive a telephone number, email, and will have access to contact support staff as needed.

When the individual is ready to confirm their willingness to participate, an electronic signature will be collected to complete the eConsent formalities. The participant will receive a copy of the fully signed HIPAA, and eConsent forms via email to retain for their records, and a digital copy will be retained within the Curebase system as part of the study records.

Upon successful documentation of informed consent, a screening video call will be performed and will serve as a baseline evaluation to confirm patient eligibility.

- Clinician Reported Outcome (ClinRO)
 - Hamilton Depression Rating Score (HDRS-17)
 - Montgomery–Åsberg Depression Rating Scale (MADRS)
 - Mini International Neuropsychiatric Interview (MINI)
 - Hamilton Anxiety Rating Scale (HAM-A)
 - Young Mania Rating Scale (YMRS)
 - Rey Auditory Verbal Learning Test (RAVLT)
- Patient Reported Outcome (PRO) Questionnaires
 - EQ-5D-3L
 - Symbol-Digit Modalities Test (SDMT)
 - Treatment Acceptability Questionnaire (TAQ)
 - tDCS Adverse Events Questionnaire (AEQ)
 - Columbia Suicide Severity Rating Scale (C-SSRS)
- Review of concomitant medications
- Final review of inclusion/exclusion criteria
- Intervention kit will be shipped to the participant

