15.5 DOCUMENTATION OF EARLY DISCONTINUATION AND PREGNANCY

In every instance where a participant does not complete the study, the Investigator will document the primary reason for discontinuation in the participant's records.

All participants are free to withdraw from participation at any time, for any reason, specified or unspecified, and without prejudice. However, if a participant expresses a desire to withdraw their consent for the study, the site should attempt to obtain written documentation for their study records.

For participants that are discontinued by the Investigator, the Investigator must notify them of their discontinuation from the study in writing.

To ensure the safety of participants who become pregnant during the study, pregnant participants will be withdrawn from the study.

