22.4 RANDOMIZATION

After a subject has met all inclusion criteria and none of the exclusion criteria, and creates an account in the Flow app, the subject will be randomized. Randomization will be performed in a 1:1 ratio to the Active and Sham groups. Randomization will be performed using randomly permuted block sizes of 4 and 6 and done independently for the two sites.

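### Pregnancy requires withdrawal for safety, but it is asked about only at screening, with no stated repeat when stimulation starts at Week 0 or Week 10

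*Protocol*

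**What the plan says.** **The rule.** Section 15.5: "To ensure the safety of participants who become pregnant during the study, pregnant participants will be withdrawn from the study". Exclusion item 30 (section 12.3) bars anyone who is pregnant or breastfeeding or plans either during the study. Item 35 extends this beyond entry: "A Subject who meets any of the exclusion criteria during study participation will be discontinued from the study". Under section 15.4, withdrawal means that the device is disabled.

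**The means of detection.** Section 14, under the pregnancy heading, states that before treatment "female participants of childbearing potential will be asked during the Screening visit whether they are pregnant or breastfeeding", or plan to be during the trial. No test and no later question is stated.

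**The two points where stimulation starts.**
- Week 0: Table 1 footnote 6 describes randomisation as "Completed after eligibility is confirmed by the investigator", and section 22.4 places it "After a subject has met all inclusion criteria and none of the exclusion criteria". Neither says when the confirmation is made or what it consists of. The "Final review of inclusion/exclusion criteria" is listed in section 13.1 (Week -3 to -1). The Week 0 list in section 13.2 has no such entry.
- Week 10: section 13.9 says that participation ends at 10 weeks "unless consented and enrolled in an additional 10-week open-label portion of the study". What that consent and enrolment step asks is not shown.

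**The concern.** A withdrawal rule of this kind protects a participant only once staff know that she is pregnant, because the device is disabled only then. The protocol states one procedure for knowing, and that procedure is finished before the first session. A participant who conceives after screening depends on some other route.

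The routes that can be seen are not aimed at pregnancy. Adverse-event recording is general, and section 19.1 defines an event as an untoward occurrence, which does not clearly prompt a report of an uncomplicated pregnancy. Concomitant-medication recording is limited by section 18 to muscle relaxation and to treatment related to MDD. Section 19.1 also treats fetal events as not anticipated, on the ground that pregnant women are excluded, so that premise rests on an answer with no stated renewal.

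Other safety exclusions are followed up. Mania (item 1) is re-checked with the YMRS, and suicidality (item 6) with the C-SSRS, at Weeks 1, 4, 7, 10 and 20. Pregnancy has its own withdrawal rule but no comparable step.

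At stake is whether the sponsor's own safeguard operates at the two moments when stimulation begins. No efficacy result is at stake.

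**Working it through.** The plan gives no figure to reproduce. The check is the age of the screening answer at each start of stimulation, from the protocol's own visit times.

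**Inputs**
- Day 0 is Week 0. Footnote 4 of Table 1 places the first stimulation session in the Week 0 onboarding.
- Screening is Week -3 to -1, ±3 days (Table 1). Footnote 5 gives the same outer limit: "Participants will be required to start treatment within 24 days from completing the baseline surveys".
- Week 10 is day 70 ± 3, so day 67 to 73. Open-label start is tied to this visit (Table 1, footnote 1). Week 20 is day 140 ± 3, so day 137 to 143.
- Assumption: the pregnancy question is asked at the screening call that also serves as baseline. If it is asked earlier, every figure below grows.

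**Age of the answer as the protocol stands**
- Earliest screening day: -21 - 3 = -24. Latest: -7 + 3 = -4.
- At first stimulation: at most 0 + 24 = 24 days, at least 0 + 4 = 4 days.
- At open-label start: at most 73 + 24 = 97 days (97/7 = 13.9 weeks), at least 67 + 4 = 71 days. On nominal Week 10 timing with the earliest screening: 70 + 24 = 94 days.
- Late visits under section 13.7 would lengthen these.

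**With the question repeated at Weeks 0 and 10**
- At first stimulation: 0 days. At open-label start: 0 days, if stimulation starts on the day of the call.
- Longest interval between questions in the blinded phase: 73 - 0 = 73 days.
- From the Week 10 question to the end of the Week 20 window: at most 143 - 67 = 76 days. No call is scheduled in between.

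**If Weeks 1, 4 and 7 are added** (windows day 4 to 10, 25 to 31 and 46 to 52), the blinded-phase intervals are at most 10 - 0 = 10, 31 - 4 = 27, 52 - 25 = 27 and 73 - 46 = 27 days. The longest falls from 73 to 27 days. The age at the two starts stays at 0.

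**The case against.** The strongest reply is that the protocol already forbids what is feared. Section 22.4 and footnote 6 require that no exclusion criterion is met at randomisation, and current pregnancy is one of them. This stands. A reader might infer that the protocol as written allows a pregnant participant to be randomised, and the documents do not support that: it would breach those rules. What remains is narrower. The protocol does not say how the investigator confirms this criterion at that time, and the only listed review of the criteria is at screening.

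A reader might also infer that nobody is asked before first stimulation. That is wrong too, since section 14 puts the question before treatment. Only the repeat is missing.

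The silence of Table 1 and the visit lists is weak evidence, because they are not exhaustive. The screening pregnancy question itself is in neither Table 1 nor section 13.1, and the MADRS-s is in Table 1 for Weeks 1, 4 and 7 but not in section 13.3. This also stands, so the point rests mainly on section 14, which names one occasion. Consent text, including that for the open-label phase, is not shown and may carry an instruction to report pregnancy. The gap at Week 10 therefore cannot be settled from the protocol alone.

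Other routes exist: self-report, adverse-event review, care by the participant's own physician (inclusion item 9) and contact between staff and providers (item 10). Item 30 keeps out those planning pregnancy. These lower the likelihood but are not stated to include a pregnancy question.

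Finally, the schedules total 36 blinded sessions (3 × 5 + 7 × 3), followed by 30 open-label sessions for former active and 36 for former sham participants. It would be tempting to read these as exposure during pregnancy. They are complete treatment courses and measure no such thing.

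**Conclusion.** The point holds as a minor one. Section 14 fixes a specific procedure that does not fully serve the safety rule in section 15.5. It is more than a detail left unsaid, and pregnancy ascertainment is protocol content rather than something left to the statistical analysis plan. Its size is the age of an answer, up to 24 days at the first start of stimulation and up to 97 days at the second. The second matters more, because a former sham participant then receives her first active course.

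These maxima combine the earliest screening day with the latest in-window visit. They measure staleness, not risk. The documents give no pregnancy rate and no data on fetal risk from the device, so no amount of harm is claimed. Sample size, type I error and the primary comparison are untouched. The conclusion at Week 0 assumes that the eligibility confirmation contains no fresh pregnancy question, and at Week 10 that the open-label consent and enrolment step contains none. If either does, what remains there is only to write it down.

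**What to change.** For participants of childbearing potential:

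1. Repeat the section 14 question on the existing Week 0 call, before account creation and randomisation.
2. Repeat it on the existing Week 10 call, before open-label stimulation starts.
3. At Week 10, tell participants to stop using the device and report promptly if they become pregnant. This part still relies on self-report, because no call is scheduled before Week 20.
4. Amend section 14 and add a row to Table 1. If the eligibility confirmation or the open-label consent already asks the question, state that there instead.

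Asking at Weeks 1, 4 and 7 as well is optional. It shortens the intervals within the blinded phase but goes beyond the two stimulation starts on which the point rests. No withdrawal rule changes.

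This is a cheap improvement: one extra question on two existing calls, one eCRF field, one table row and one sentence in the Week 10 script. It needs no new visit, test or staff.

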15 EARLY DISCONTINUATION: PARTICIPANTS

15.1 TECHNICAL FAILURES

In case the Flow device or the participant's smartphone breaks, and it cannot be replaced within 10 days, and the participant has not already completed 22 sessions, this will be considered a technical failure, and the participant will be withdrawn from the trial.

